A Introduction

A1 Study Abstract:

This study will use non-invasive MR scanning to help answer questions related to brain function and development in children suffering from craniosynostosis. Craniosynostosis affects roughly 1 in 2000 children. Primary indication for operative treatment for patients with craniosynostosis is to prevent or treat increased Intra-Cranial Pressure (ICP) and avoid neurological impairment. Increased ICP is thought to result from restricted space for brain growth caused by the abnormal cranial vault. However, the literature on the relationship between craniosynostosis and ICP is limited. Due to the invasiveness of the test, preoperative ICP monitoring is not routinely performed to decide if operative repair is required. Other indirect signs of elevated ICP have been described but are not reliable.

While it is not currently feasible to measure ICP directly, we may be able to indirectly determine ICP in children via magnetic resonance imaging (MRI). We aim to compare the assessment of ICP with the conventional, invasive intraventricular shunt to an indirect assessment of ICP via MRI.

Ten children with an intraventricular shunt will be enrolled in this pilot study over a one-year period. We will obtain indirect measures of ICP. The results will be compared to ICP measures obtained via the shunt.

Ultimately the assessment of ICP using MRI in patients with craniosynostosis may revise surgical indications and timing of surgery, potentially changing the standard of care for patients with craniosynostosis. Additionally, this approach might be used for patients with other diagnoses which impact ICP.

A2 Primary Hypothesis

Indirect (via MRI) and direct measures of ICP will have a significant positive correlation.

A3 Purpose of the Study Protocol

The purpose of this study is to evaluate the use of magnetic resonance imaging (MRI) to determine intra-cranial pressure in young children.

B Background

B1 Prior Literature and Studies

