Although multiple tests have been suggested to assess ICP in patients with craniosynostosis, including papilledema and copper beaten appearance of the skull on plain film, none have been shown to be reliable measures or markers of ICP. Recent advances in MRI suggest that ICP can be indirectly measured with this modality non-invasively and with minimal patient risk.

D Investigational Agent

D1 Clinical Data to Date

The MR sequences for this study have been used in studies of traumatic brain injury. To our knowledge these sequences have not yet been used for patients with craniosynostosis.

D2 Dose Rationale and Risk/Benefits

The main risk of the MR scan in this population is the feeling of being closed in or discomfort from lying still. This is an acceptable risk given the benefit of obtaining hard evidence of brain stress in subjects with synostosis. The time patients are in the scanner (approximately 45 minutes) has been adequate to obtain useful data in populations of minors post traumatic brain injury and normal controls. These tests were performed by Drs. [name] and [name].⁷

E Study Design

E1 Overview or Design Summary

Up to 12 patients with craniosynostosis will be enrolled in this pilot study. Various measures of cerebral metabolism and perfusion will be taken during a single visit via MR scanning.

The results may also be compared to age and gender matched normative data. These controls will be recruited in the plastic surgery clinic and/or deidentified data from normal subjects from another study will be used. Participation in this research study consists of one to two parts. First, all patients will be asked to extend a clinical visit for MRI. During this time the intra-cranial pressure MRI testing will be done, lasting approximately 10 minutes. The scan will be performed in the radiology center on the 1st floor of Children's Hospital. The clinical scan will be done under sedation. Secondly, during the same visit, a transducer will be attached to the participant's intraventricular catheter if it is not already in place. The patients ICP will be measured directly with this transducer. Subjects have no further commitment once the scan (and ICP measurement) is complete.

E2 Subject Selection and Withdrawal

2.a Inclusion Criteria

- Subjects presenting to the Plastic Surgery clinic with unrepaired single-suture craniosynostosis.
- Age-matched controls

Exclusion Criteria

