MR spectroscopy (MRS) will be used to obtain concentrations of N-acetyl aspartate (NAA) and lactate. NAA is a highly sensitive marker of brain injury and the presence of lactate can indicate compromised metabolism. We will measure whole-brain oxygen extraction (OEF) using a magnetic field mapping approach. Elevated OEF is a key indicator of compromised perfusion. Cerebral blood flow (CBF) will be measured using an arterial spin labeling (ASL) sequence, which will allow direct measurement of perfusion deficiencies. We will also obtain functional connectivity data using an rfcMRI sequence, which is sensitive to developmental delay. The analysis for OEF and ASL data will be performed by [name]. The MRI images will be read by [name], Chief of Radiology at Saint Louis Children's Hospital. Measures will include location and severity of metabolic effects, size of the optic nerve sheath, and cerebral perfusion.

G Statistical Plan

G1 Sample Size Determination and Power

As this is a pilot study there is no relevant data to determine the power of this study. The data collected here will be used as a guide for sample size determination of future studies.

G2 Interim Monitoring and Early Stopping

N/A

G3 Analysis Plan

The data obtained from the pilot study will be evaluated for patterns in the data between the subjects with craniosynostosis and the matched controls.

G4 Statistical Methods

Various graphical and image analysis approaches will be applied to tease out potential patterns between cases and controls and between the affected and unaffected sides of patients with unilateral craniosynostosis.

H Data Handling and Record Keeping

H1 Confidentiality and Security

Privacy during the recruitment and consent process will be protected by performing these procedures in private patient rooms in the hospital or clinic setting.

The MRI will be performed in the Center for Clinical Imaging Research (CCIR). No unnecessary PHI will be collected. Data will be a coded.

H2 Training

All members of the research team will be familiar with this protocol and the standard prosecution of clinical trials.

H3 Records Retention

Patient records will be stored behind a double lock system in the craniofacial laboratory in the division of Plastic Surgery.

I Study Administration

I1 Organization and Participating Centers

Division of Plastic Surgery in cooperation with the Department of Radiology

I2 Funding Source and Conflicts of Interest

None at this time.

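### Section G plans no analysis of MRI against direct ICP, which is the study's only hypothesis, and no section says which MRI quantity is the indirect ICP measure

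*Combined protocol and SAP*

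**What the plan says.** - **Hypothesis (A2).** "Indirect (via MRI) and direct measures of ICP will have a significant positive correlation". No other hypothesis is stated.
- **Intended comparison (A1).** Of the indirect MRI measures, A1 says: "The results will be compared to ICP measures obtained via the shunt". It names neither the MRI variable nor a method.
- **Measurements (E1).** "During this time the intra-cranial pressure MRI testing will be done, lasting approximately 10 minutes". The output of that test is not given. At the same visit a transducer on the intraventricular catheter is to give direct ICP.
- **Schedule and outcomes (F2, F4).** F2 describes a single visit made up of the MR scan. F4 lists NAA, lactate, OEF, CBF, functional connectivity and optic nerve sheath size. Direct ICP is in neither section.
- **Analysis (G3, G4).** G3: "The data obtained from the pilot study will be evaluated for patterns in the data between the subjects with craniosynostosis and the matched controls". G4 applies graphical and image methods to that contrast and to affected versus unaffected sides in unilateral cases.
- **Status of the control comparison (E1).** "The results may also be compared to age and gender matched normative data", so it is optional there.
- **Who is enrolled.** A1: "Ten children with an intraventricular shunt will be enrolled in this pilot study over a one-year period". E1: "Up to 12 patients with craniosynostosis will be enrolled in this pilot study". E2 asks for unrepaired single-suture disease, has no catheter criterion, and excludes other abnormalities affecting the brain.

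**The concern.** The plan analyses a comparison that E1 treats as optional and leaves out the one the study was set up to make. A difference between cases and controls, or between sides, may serve the aim in D2 of "obtaining hard evidence of brain stress in subjects with synostosis". It does not show that an MRI measure rises and falls with ICP, because direct ICP enters neither contrast.

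Two further consequences follow. G1 says the pilot data will guide the size of later studies, but Section G plans no estimate of the MRI-ICP relationship to guide a study of that relationship. And with no MRI index named, a correlation added later could be run on several measures and the most favourable one reported as the test of A2.

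**Working it through.** The documents give no alpha, sidedness, effect size or derivation of the sample size, so there is no stated figure to reproduce. The main check is of the text; the arithmetic only illustrates the consequences.

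**1. Does any planned analysis use direct ICP?**

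| Planned contrast | Source | Uses direct ICP? |
|---|---|---|
| Cases vs matched controls | G3, G4 | No |
| Affected vs unaffected side | G4 | No |

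The count is 0 of 2. G1 to G4 mention neither ICP, the shunt, the transducer, correlation nor agreement.

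**2. Is the MRI side of the pair identified?** E1's ICP test has no stated output. F4 presents its measures as markers of injury, metabolism, perfusion or development, and lists optic nerve sheath size without a rationale. None is designated as indirect ICP. The expected sign is not settled either: F4 treats raised OEF and the presence of lactate as adverse, but for CBF a deficiency is adverse. A positive correlation has no definite meaning until one index and its direction are fixed.

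**3. How many pairs could there be?** The number is 0 if no enrolled child has a catheter, which E2 permits; 10 if A1 is followed and every child is measured both ways; and 12 if all of E1's maximum have a catheter and both measurements.

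**4. Cost of leaving the index open (illustration).** Assume each of the six F4 measures listed above is correlated with direct ICP at 5%. Six is my count; no section plans six tests.

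- Two-sided tests, only positive results counted (0.025 each): 1 − 0.975^6 = 0.141 if independent; at most 6 × 0.025 = 0.15 under any dependence.
- One-sided tests (0.05 each): 1 − 0.95^6 = 0.265 if independent; at most 6 × 0.05 = 0.30.

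**5. Precision once the analysis is added.** Fisher z interval for Pearson r, one pair per child, with an assumed observed r = 0.70: tanh(atanh(0.70) ± 1.96/√(n − 3)), where atanh(0.70) = 0.867.

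- n = 10: 0.867 ± 1.96/√7 = 0.867 ± 0.741, giving 0.13 to 0.92.
- n = 12: 0.867 ± 1.96/√9 = 0.867 ± 0.653, giving 0.21 to 0.91.
- n ≤ 3: the interval is undefined.

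These intervals show what the repaired analysis could deliver. They do not measure the size of the defect.

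**The case against.** The strongest reply is that the comparison is already in the document. A2 names a correlation and its direction, A1 names a set of children and says the results will be compared with shunt readings, and F4 can be read as the list of indirect measures. E1 collects the direct reading, so where a catheter exists the pairs would exist and could be analysed. The study is also a small pilot with no power claim.

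Part of this stands. The intent is clear, and the missing estimate is unplanned rather than unobtainable. A pilot could also reasonably report several prespecified measures with intervals instead of one. But no sentence says that the F4 list is the set of indirect ICP measures, A1's set conflicts with E1 and E2, and G4 confines its graphical methods to the two contrasts above. Pilot status explains the absence of a power calculation. It does not explain the absence of any planned estimate for the sole hypothesis.

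The illustration in step 4 is also open to challenge. The number of measures is a judgement: connectivity is not a single number, for example. The 14% figure and its 15% bound hold only if the supporting sign of each measure is fixed beforehand. If either sign could be presented as support, two-sided testing gives 26.5%, with a bound of 30%.

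**Conclusion.** The concern holds and must be fixed. None of the planned contrasts addresses A2, direct ICP is not a listed outcome, and the indirect measure is not designated, so the analysis as written cannot answer the study's question. This conclusion rests on the text alone and needs no numerical assumption.

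The 14% to 30% range for a false supportive result assumes six tests at 5%. The intervals assume Pearson r, an observed value of 0.70, and 10 or 12 complete pairs. The current text guarantees no particular number of pairs between 0 and 12.

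**What to change.** 1. In G3 and G4, make the primary analysis a paired one in all children with both measurements: a scatterplot of the MRI index against direct ICP in mmHg, and one named correlation coefficient with its 95% CI. State the rule that gives one ICP value per child. If the index is itself on a pressure scale, add an agreement analysis.
2. Name the single MRI index, either the output of the E1 ICP test or one F4 measure if that is what is meant. State its units and expected sign, list it in F4, and call the other MRI measures exploratory.
3. List direct ICP in F2 and F4.
4. Label the case-control and side-to-side contrasts secondary.
5. Reconcile A1 with E1, E2 and the recruitment text in 2.b on who is enrolled and whether a catheter is present, and state the expected number of pairs.

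Items 1 to 4 cost rewording of F2, F4, G3 and G4 and a little analysis work, since E1 already plans the direct reading. Item 5 may require changes to eligibility and recruitment text: recruitment is through Plastic Surgery with no catheter criterion, and the exclusion for other abnormalities could remove shunted children. Items 1 to 4 yield a usable estimate only once item 5 is settled, and with 10 to 12 pairs that estimate will still be imprecise.
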